9.3.3 Demographic and Baseline Characteristics

Descriptive statistics of demographics (sex, age, race) and baseline characteristics (height, weight) will be presented.

9.3.4 Immunogenicity Analysis

Analysis for immunogenicity against Polio

Seroconversion rate and sero-protection rate on day 28 after the last vaccination of sIPV will be estimated, and the corresponding 95% CIs will be derived from Clopper Pearson method.

The difference of seroconversion rates between co-administration group and staggered administration group will be compared using Cochran-Mantel-Haenszel- χ^2 (CMH- χ^2) test stratified by study site. The CMH- χ^2 method will be used to calculate the rate difference between (group C1 and group S1) and 95% CIs. Non-inferiority will be concluded if the lower limit of the 95% CI of rate difference (co-administration group-staggered administration group) $>-10\%$.

The descriptive statistics, including GMT and GMFR and corresponding 95% CIs are employed to summarize the immunogenicity data. The t-tests after log transformation will be used to compare two groups. The GMT ratio between two groups and the corresponding 95% CIs will be estimated as well.

Analysis for immunogenicity against Diphtheria, Tetanus, Pertussis

Seropositivity/sero-protection rate against Diphtheria, Tetanus and Pertussis on day 28 after the last vaccination of DTP-HepB-Hib vaccine will be estimated and the corresponding 95% CIs will be derived from Clopper Pearson method. The difference of seropositivity/sero-protection rate between co-administration group and staggered administration group will be Cochran-Mantel-Haenszel- χ^2 (CMH- χ^2) test stratified by study site. The CMH- χ^2 method will be used to calculate the rate difference between (group C2 and group S2) and 95% CIs. Non-inferiority will be concluded if the lower limit of the 95% CI of rate difference (co-administration group-staggered administration group) $>-10\%$.

The descriptive statistics, including GMC and GMFR and corresponding 95% CIs are employed to summarize the immunogenicity data. The t-tests after log transformation will be used to compare two groups. The GMC ratio of two groups and the corresponding 95% CIs will be estimated as well.

Analysis for immunogenicity against HepB, Hib, Pneumococcal

Sero-protection rates at day 28 after the last vaccination will be estimated and the corresponding 95% CIs will be derived from Clopper Pearson method. The Chi-square tests/Fisher Exact test will be used

to compare the sero-protection rates between two groups.

The descriptive statistics including GMC and GMFR and corresponding 95%CIs are employed to summarize the immunogenicity data. The t-tests after log transformation will be used to compare two groups.

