3. OBJECTIVES AND ENDPOINTS

The objectives and endpoints of this clinical trial are as follows:

	Objectives	Endpoints
Primary	To evaluate the non-inferiority of immune response to polio vaccination, when administered concomitantly with routine vaccines	
 Seroconversion rates of neutralizing antibody against polioviruses of three serotypes, at 28 days after three doses of vaccination
	To evaluate the safety in terms of ARs (Vaccine-related AEs)	
 Incidence of adverse reactions within 7 days after each dose of vaccination
Secondary	To evaluate non-inferiority of immune response to diphtheria and tetanus antigens, when routine vaccines are administered concomitantly with sIPV	
 Sero-protection rate of IgG antibodies against diphtheria (DT) and tetanus (TT), at 28 days after vaccination
	To evaluate non-inferiority of immune response to acellular pertussis antigens, when routine vaccines are administered concomitantly with sIPV	
 Seropositivity rate of IgG antibodies against pertussis toxin (PT), Filamentous hemagglutinin (FHA), Pertactin (PRN), at 28 days after vaccination
	To evaluate other immunogenicity against diphtheria, tetanus, acellular pertussis antigens	
 GMC/GMFR of IgG antibodies against DT, TT, PT, FHA, PRN, at 28 days after vaccination
	To evaluate other immunogenicity of sIPV, when administered concomitantly with routine vaccines	
 Sero-protection rate of neutralizing antibody against polioviruses of three serotypes, at 28 days after three doses of vaccination GMT/GMFR of neutralizing antibodies against polioviruses of three serotypes, at 28 days after three doses of vaccination
	To evaluate the immunogenicity against hepatitis B and Hib, when routine vaccines are administered concomitantly with sIPV	
 Sero-protection rate of IgG antibodies against hepatitis B and Hib, at 28 days after vaccination GMC/GMFR of IgG antibodies against hepatitis B and Hib, at 28 days after vaccination
	To evaluate the immunogenicity against pneumococcal, when routine vaccines are administered concomitantly with sIPV	
 Sero-protection rate of IgG antibodies against pneumococcal, at 28 days after vaccination GMC/GMFR of IgG antibodies against pneumococcal, at 28 days after vaccination

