The reverse cumulative distribution plot of antibody titers at pre- and post-vaccination time points will be plotted.

The above analysis will be based on the FAS and PPS.

➤ **Immunogenicity evaluation for IgG antibodies against pertussis**

The following analysis will be performed for IgG antibodies against PT, FHA and PRN of **group C2 and group S2 at 28 days after last vaccination of DTP-HepB-Hib**, respectively:

The seropositivity rate and SCR for all participants will be estimated by groups. The Clopper Pearson method will be used to calculate 95% CIs and the CMH- χ^2 test considering the study site (including Bangladesh 01, Pakistan 01 and Pakistan 02) as a stratification factor will be used to test the differences between groups. The CMH- χ^2 method will be used to calculate the rate difference between (group C2 - group S2) and 95% CIs.

Analysis of covariance model will be modeled to analyze IgG antibody level against PT, FHA and PRN at 28 days after last vaccination of DTP-HepB-Hib. In this model, the log-transformed IgG antibody data against PT, FHA and PRN at 28 days after last vaccination of DTP-HepB-Hib will be included as dependent variable, the log-transformed IgG antibody data before vaccination as a covariate, and treatment group (including C2 and S2) and study site (including Bangladesh and Pakistan) are the fixed effect. From the model, the LS-adjusted log-transformed IgG antibody level against PT, FHA and PRN at 28 days after last vaccination of DTP-HepB-Hib in each group and the difference between (group C2 - group S2) will be calculated. The adjusted GMC at 28 days after last vaccination of DTP-HepB-Hib in each group, GMC ratio between (group C2/group S2), and its 95% CIs will be obtained after inverse log-transformation.

Descriptive statistics, including geometric mean and 95% CIs, for GMC and GMFR of all participants will be presented by groups. The grouped t-test after log-transformation will be used to compare the differences between groups. The ratio of GMC between groups and their 95% CIs will be estimated as well.

The reverse cumulative distribution plot of antibody concentrations at pre- and post-vaccination time points will be plotted.

The above analysis will be based on the FAS and PPS.

➤ **Immunogenicity evaluation for IgG antibodies against diphtheria, tetanus, HepB, Hib and pneumococcal**

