The following analysis will be performed for IgG antibodies against diphtheria, tetanus, HepB, Hib and pneumococcal (including serotypes of 1, 5, 6B, 14 and 19F) of **group C2 and group S2 at 28 days after last vaccination of DTP-HepB-Hib and PCV**, respectively:

The SPR for all participants will be estimated by groups. The Clopper Pearson method will be used to calculate 95% CIs and the CMH- χ^2 test considering the study site (including Bangladesh 01, Pakistan 01 and Pakistan 02) as a stratification factor will be used to test the differences between groups.

Analysis of covariance model will be modeled to analyze IgG antibodies against diphtheria, tetanus, HepB, Hib and pneumococcal (including serotypes of 1, 5, 6B, 14 and 19F) at 28 days after last vaccination of DTP-HepB-Hib. In this model, the log-transformed IgG antibodies against diphtheria, tetanus, HepB, Hib and pneumococcal (including serotypes of 1, 5, 6B, 14 and 19F) at 28 days after last vaccination of DTP-HepB-Hib will be included as dependent variable, the log-transformed IgG antibody data before vaccination as a covariate, and treatment group (including C2 and S2) and study site (including Bangladesh and Pakistan) are the fixed effect. From the model, the LS-adjusted log-transformed IgG antibodies against diphtheria, tetanus, HepB, Hib and pneumococcal (including serotypes of 1, 5, 6B, 14 and 19F) at 28 days after last vaccination of DTP-HepB-Hib in each group and the difference between (group C2 - group S2) will be calculated. The adjusted GMC at 28 days after last vaccination of DTP-HepB-Hib in each group, GMC ratio between (group C2/group S2), and its 95% CIs will be obtained after inverse log-transformation.

Descriptive statistics, including geometric mean and 95% CIs, for GMC and GMFR of all participants will be presented by groups. The grouped t-test after log-transformation will be used to compare the differences between groups. The ratio of GMC between groups and their 95% CIs will be estimated as well.

The reverse cumulative distribution plot of antibody concentrations at pre- and post-vaccination time points will be plotted.

The above analysis will be based on the FAS and PPS.

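### Sero-protection against hepatitis B, Hib and five pneumococcal serotypes is compared between C2 and S2 by a test of difference, with no rate difference and 95% CI planned

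*Protocol*

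**What the plan says.** Protocol section 3 makes these rates secondary endpoints, for example "Sero-protection rate of IgG antibodies against pneumococcal, at 28 days after vaccination", with a matching entry for hepatitis B and Hib. With five serotypes tested, that gives seven rates. The objectives ask for an evaluation of immunogenicity under co-administration and do not mention non-inferiority.

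For these antigens Protocol 9.3.4 plans a one-arm estimate, "Sero-protection rates at day 28 after the last vaccination will be estimated and the corresponding 95% CIs will be derived from Clopper Pearson method", and then a comparison: "The Chi-square tests/Fisher Exact test will be used". The block on diphtheria, tetanus and pertussis just above it goes further: the CMH "method will be used to calculate the rate difference between (group C2 and group S2) and 95% CIs", with a -10% criterion. Polio seroconversion is treated in the same way.

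SAP 7.7 puts diphtheria, tetanus, hepatitis B, Hib and pneumococcal in one block. "The SPR for all participants will be estimated by groups", with Clopper-Pearson intervals, and a CMH test with study site "as a stratification factor will be used to test the differences between groups". No rate difference follows. The pertussis block before it does have one: the CMH "method will be used to calculate the rate difference between (group C2 - group S2) and 95% CIs". On the concentration scale the SAP plans, for all these antigens, a C2/S2 GMC ratio adjusted for baseline and site with a 95% CI, and also an unadjusted one: "The ratio of GMC between groups and their 95% CIs will be estimated as well".

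**The concern.** The trial exists because data on giving sIPV together with routine infant vaccines are lacking (Protocol 2.1). For these seven rates the useful result is the size of C2 minus S2 and the largest loss the data rule out. A test of equality supplies neither. A p-value above 0.05 may reflect no interference or too little information. A p-value below 0.05 may reflect a difference too small to matter.

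If the report follows the plan literally, the only formal comparison of these proportions is a p-value. A later author could then write that co-administration did not affect sero-protection on evidence that still allows a loss of more than 10 points.

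**Working it through.** **1. The passages side by side: is a between-arm rate difference with 95% CI planned?**

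| Antigen | Protocol 9.3.4 | SAP 7.7 |
|---|---|---|
| Polio seroconversion | yes | yes |
| Pertussis | yes | yes |
| Diphtheria, tetanus | yes | no |
| HepB, Hib, pneumococcal | no (chi-square/Fisher) | no (stratified CMH test) |

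**2. The plan's own sample size (polio only).** Inputs from Protocol 9.1: control rate 90%, margin -10 points, one-sided 0.025, power 1 - 0.20/3 = 0.933, ratio 1:1. The Farrington-Manning score formula uses rates restricted to the margin, 0.831 and 0.931:

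n = [(1.960 × √0.2042 + 1.501 × √0.18) / 0.10]² = 231.8, so 232 against the stated 233. This reproduces the figure closely. No power, margin or expected rate is given for the seven rates considered here.

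**3. Evaluable number per arm.** 360 enrolled, 15% dropout and 10% blood collection failure (Protocol 9.1): 360 × 0.85 × 0.90 = 275.4, taken as 275.

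**4. How often the test misses a real drop.** The documents give no control rates for these antigens, so a range is assumed. For control rate p2, co-administration rate p1 = p2 - d and average p̄:

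- s0 = √[2p̄(1 - p̄)/n]
- s1 = √[p1(1 - p1)/n + p2(1 - p2)/n]
- power = Φ[(d - 1.96 × s0)/s1]

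Example, 90% to 85%: s0 = 0.02820, s1 = 0.02812, (0.05 - 0.05527)/0.02812 = about -0.19, power 0.426, missed 57%.

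| Control rate | 5-point drop missed | 10-point drop missed | 95% CI half-width at equal rates (points) |
|---|---|---|---|
| 80% | 71% | 23% | 6.7 |
| 90% | 57% | 9% | 5.0 |
| 95% | 40% | 2% | 3.6 |
| 98% | 19% | 0.4% | 2.3 |

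The half-width is 1.96 × √[2p2(1 - p2)/n].

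Sensitivity to n, 5-point drop missed, for control rates of 80%, 90%, 95% and 98%:
- 233 per arm: 75%, 63%, 46%, 26%
- 360 per arm: 64%, 47%, 28%, 10%

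**5. What a single result could look like.** Invented counts with 275 per arm, Pearson chi-square p-value and Miettinen-Nurminen 95% CI for C2-S2:

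| S2 | C2 | p | 95% CI (points) |
|---|---|---|---|
| 220/275 (80.0%) | 201/275 (73.1%) | 0.056 | -14.0 to +0.2 |
| 248/275 (90.2%) | 233/275 (84.7%) | 0.053 | -11.1 to +0.1 |
| 261/275 (94.9%) | 250/275 (90.9%) | 0.068 | -8.5 to +0.3 |
| 270/275 (98.2%) | 261/275 (94.9%) | 0.036 | -6.8 to -0.2 |

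The first two are not significant, yet do not exclude the 10-point loss used as the criterion for other antigens. The last is significant, yet lies wholly inside 10 points. The p-value can mislead in either direction.

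These calculations are unstratified. A site-stratified analysis should behave similarly unless rates differ strongly between sites.

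**The case against.** The strongest reply is that the comparison is not left to a p-value alone. Each arm's rate comes with an exact interval, so the point difference is a subtraction and a crude interval follows from the counts. SAP 7.7 plans reverse cumulative distribution plots which, if drawn by group, show the proportion above any cutoff. It also plans adjusted and unadjusted GMC ratios with 95% CIs for exactly these antigens. All of this stands. A reader might infer that the p-value will be the only between-group evidence, and the documents do not support that.

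A reader might also infer that the plan treats p>0.05 as showing no interference. It contains no such rule. These endpoints carry no non-inferiority hypothesis, margin or power claim, so no confirmatory conclusion is at risk.

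The miss rates also depend on the assumed control rate. A 10-point drop is rarely missed from 90% or above, and the 23% figure is the least favourable of those shown.

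What survives is narrower. A GMC ratio does not say how many infants fall below 10 mIU/ml, 0.15 µg/mL or 0.35 µg/mL, and Protocol 9.3.4 does not list even that ratio for these antigens. A difference worked out from the published counts would ignore site, although the SAP's own test is stratified by site. The SAP mock-up shells are not among the documents, so it cannot be ruled out that a difference column appears there.

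**Conclusion.** The concern holds as a gap in estimation. For seven secondary sero-protection rates neither document's text plans the C2-S2 difference with a 95% CI, while both plan it for polio and pertussis and the protocol also plans it for diphtheria and tetanus. The consequence is that a loss in the protected proportion is less precisely quantified; no confirmatory decision changes.

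With about 275 evaluable per arm, the two-sided 5% test misses a true 5-point drop between 19% (from 98%) and 71% (from 80%) of the time, and a 10-point drop between 0.4% and 23%. The control rates are assumptions, and 275 assumes that the planned losses occur. If observed rates are close to 100%, the practical effect is small. The change is worth making because it costs almost nothing and answers the co-administration question directly.

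**What to change.** In Protocol 9.3.4 (hepatitis B, Hib, pneumococcal) and in the corresponding block of SAP 7.7, add the site-stratified CMH estimate of the C2-S2 sero-protection difference with its 95% CI for hepatitis B, Hib and serotypes 1, 5, 6B, 14 and 19F. The sentence in the SAP's pertussis block can be reused. Label the estimate descriptive, with no margin, and state that the comparison is interpreted from the interval and not from a non-significant p-value.

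At the same time, name one test in both documents. The protocol has chi-square/Fisher and the SAP has CMH, although SAP 2.3 describes the analyses as consistent with the protocol. Because the SAP block is shared, the same sentence would also supply the diphtheria and tetanus difference that the protocol already requires.

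Cost: one sentence in each document and two table columns. No new data, participants or alpha adjustment are needed.

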9.3.5 Safety Analysis

Treatment-emergent adverse events (TEAEs) are defined as any AEs that occurred on or after vaccination date or worsening of existing events. AEs will be coded using the Medical Dictionary for Regulatory Activities (MedDRA), version 25.0 or later version.

TEAEs will be summarized by frequency and percentage, and tabulated by system organ class (SOC) and preferred term (PT). Serious adverse events (SAEs) will also be summarized.

The following summary tables and patient level listings will be presented for TEAE data:

- Overall Summary of Adverse Events
- TEAEs by SOC and PT
- TEAEs by SOC and PT, Related to Vaccination
- TEAEs by SOC and PT, Unrelated to Vaccination
- TEAEs by SOC, PT and Severity
- TEAEs by SOC, PT and Severity, Related to Vaccination
- TEAEs by SOC, PT and Severity, Unrelated to Vaccination
- TESAEs by SOC and PT
- TESAEs by SOC and PT, Related to Vaccination
- TESAEs by SOC and PT, Unrelated to Vaccination
- Listing of SAEs
- Listing of Related SAEs
- Listing of AEs

9.4 Subgroup Analysis

No subgroup analysis will be conducted in this study.

9.5 Multiplicity

The primary hypothesis will be achieved only when the non-inferiority of seroconversion rates against all poliovirus type 1, 2 and 3 are all concluded. Thus, the family-wise type I error will not be inflated.

9.6 Method of Missing Data Handling

In immunogenicity analysis, the missing values in post-vaccination antibody data will be imputed by using the Last Observation Carried Forward (LOCF) method. The details in missing data handling will be described in the statistical analysis plan (SAP).

10. DATA COLLECTION AND MANAGEMENT

10.1 Data Collection

eCRFs will be used for recording data for each participant enrolled in the study. The site investigators are responsible to ensure the accuracy, completeness, legibility, and timeliness of the data captured in eCRF. Data captured in the eCRF derived from source documents and should remain consistent with those source documents. In case of discrepancies, data will be clarified and corrected.

Study staff will extract all data collected in source documents and workbooks for entry into the eCRF. An Electronic Data Capture (EDC) system is a software that will be used to store the participant's data collected in this study. The EDC is a web-based application to capture data for clinical research and

create databases and projects. It is highly secure and intuitive to use. A unique username issued by clinical data management provider and an associated password will be required to log into the EDC system to access study data. This server is 24hrs online, fault tolerant and automatic back-up system. There is a logging system for collecting every event/action with logs recorded in the system. At the user end, we have daily, weekly, and monthly back-up system to back-up all the data in a local computer. The data will be stored in a main server found in China. Data can be downloaded from the server in SAS/CSV/PDF format as per project need. The entire data collection and handling will be monitored to ensure database integrity. Edit checks will be programmed in the EDC to identify data entry errors during transcription, including range and consistency checks wherever applicable.

Final data cleaning, data freezing, and data analysis will be performed by sponsor/vendor. All data will be stored in a secure database.

10.2 Safety Follow-up Method

AEs/SAEs will also be followed up at site visits and subject diaries will be given to all participants before each dose of vaccination. Diary cards will be distributed to guardians of participants to record AEs from the time of first vaccination to 28 days after last vaccination. Diary cards will be delivered by the study staff after the vaccination on V1 (day 0). The diary card will be filled in every day from the next day after each vaccination until the 7th day after the booster vaccination. From the 8th day until the 14th day after each dose (until 28th day for co-administration group and last dose of staggered administration group), AEs (if occurred) will be recorded by the guardians of participants on the diary card.

For the concomitant vaccination group: on the 14th day after each vaccination, study staff will call guardians of participants to verify the completeness of the diary card; on the 28th day after each vaccination, study staff will make a face-to-face interview to the guardians of participants with the diary card brought back, to check the completeness of the diary card.

For the staggered vaccination groups: on the 14th day after each vaccination and 28th day after last vaccination, study staff will make a face-to-face interview to the guardians of participants with the diary card brought back, to check the completeness of the diary card.

10.3 Study Records Retention

The site investigators (SI) will retain all study records that support eCRFs for this study (i.e., ICFs, source documents, investigational product dispensing records) required by sponsor and by the applicable regulations in a secure and safe facility. The SI will consult sponsor/representative before disposal of any study records and will notify the sponsor of any change in the location, disposition, or custody of the study files. These documents should be retained for at least 5 years after the study completion.

10.4 Publication and Data Sharing

After the completion of this clinical trial, if the results of the trial need to be disclosed and/or published, the positive results will be disclosed and/or published together with the negative results.

11. QUALITY ASSURANCE

11.1 General Consideration

Quality Assurance (QA) oversight will be implemented at all stages of the trial process per ICH E6 (R2) section 5.0 and/or local government GCP requirements.

Quality Control (QC) procedures will be implemented beginning with the data entry system and data QC checks that will be run on the database will be generated. Any missing data or data anomalies will be communicated to the site(s) for clarification/resolution.

The site will also develop routine operational checks to verify that critical protocol requirements and procedures are executed correctly and completely at the time the work is being performed.

The investigational site will provide direct access to all study related documents, source data/documents,

and reports for the purpose of monitoring and auditing by the sponsor, and inspection by local and regulatory authorities.

